### 5.7.2 Safety

#### Missing/Partial Start Date for AEs

The following rules will be applied to missing or incomplete start dates when determining if an AE is treatment emergent. The rules will be applied first before determining the treatment emergent status and imputed dates will be treated as complete dates for this purpose. These rules are intended to lead to a conservative assessment of treatment emergence. The imputed dates are only used for determining treatment emergence and the recorded partial dates will be displayed in listings. The same rules will be applied for prior and concomitant medications as per [section 5.4](#).

If the year of onset of the AE is missing, then the AE is considered treatment emergent.

If the year of the AE onset date is complete, but the month and day of the onset of the AE are missing, then the following rules apply:

- If the year of the AE is the same as the year of the study treatment administration then the AE is considered treatment emergent, and the AE onset date will be set to the study treatment administration date.
- If the year of the AE onset date is after the year of study treatment administration, then the date is set to 01 January and the AE is considered treatment emergent.
- If the year of the AE onset date is before the year of study treatment administration date, then the AE is not treatment emergent.

If the year and month of the AE onset date are complete, but the day of the onset of the AE is missing, then the following rules apply:

- If the year and month of the AE onset date is the same as the year and month of the treatment administration date, then the AE is considered treatment emergent and the AE onset date will be set to the treatment administration date.
- If the year and the month of the AE onset date are complete, and the month of the AE onset date is after the month of the study treatment administration date, then the day of the AE onset date will be set to the first day of the month. The AE will be assigned as treatment emergent.
- If the year and the month of the AE onset date are before the year and the month of treatment administration date, then the AE is not treatment emergent.

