## ETDRS/LogMAR and on-chart and off-chart:

- I. 1 ETDRS line = 5 letters
- II. 1 ETDRS line = 0.1 LogMAR
- III. 0.1 LogMAR = 5 ETDRS letters
- IV. 15 ETDRS letters = 0.3 LogMAR
- V. A less positive/more negative LogMAR is an improvement of vision
- VI. An increase in the number of ETDRS letters read is an improvement of vision

On-Chart subjects: defined as being able to read at least 3 ETDRS letters on a single line on the ETDRS chart at either 4 or 1 meters

- a. Have an obtainable Snellen equivalent obtained directly from ETDRS chart
- b. Each Snellen equivalent is assigned a LogMAR value

Off-chart Subjects: defined as a subject who cannot read at least 3 ETDRS letters on a single line of the ETDRS chart at either 4 or 1 meters and thus have no Snellen equivalent obtainable from ETDRS chart

- c. These subjects are categorized as able to either count fingers (CF), detect hand motion (HM), detect light perception (LP) or are no-light perception (NLP)
- d. For those categorized as either CF or HM a method for deriving LogMAR visual acuity is pre-specified
- e. The distance at which CF/HM vision was obtained is recorded per the standard operating procedure
- f. Study database derives the LogMAR based on this distance and the finger/hand dimensions of the examiner, per pre-specified method.

Treatment-Emergent Adverse Events (TEAE)

Treatment-emergent adverse events (TEAEs) are defined as AEs that started after study treatment administration at Visit 3 or that represent an exacerbation of a condition that is present at baseline after treatment administration. Worsening of visual acuity determined by the investigator to be due to progression of LHON will not be considered as an AE. Any AE with an unknown start date will be considered treatment-emergent if the event does not stop prior to study treatment administration. AEs with partial dates are described in [Section 5.7.2](#).

Prior and Concomitant Treatment

Prior treatments will be defined as any treatments with start date and time prior to the study treatment administration date and time.

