#### Missing/Partial End Date for AEs

If the end date is missing and the start date is on or after the date of treatment administration, then the AE is considered treatment emergent

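### SAP 5.7.2 assigns treatment-emergent status without checking the stop date; it contradicts SAP 5.6 for AEs of wholly unknown onset and misflags some partly dated AEs that ended before injection

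*SAP*

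**What the plan says.** SAP 5.6 (Derived Variables, Treatment-Emergent Adverse Events) gives the basic definition: "Treatment-emergent adverse events (TEAEs) are defined as AEs that started after study treatment administration at Visit 3". A post-dose exacerbation of a condition present at baseline also counts. For onset that is not known at all, it adds: "Any AE with an unknown start date will be considered treatment-emergent if the event does not stop prior to study treatment administration". For onset that is partly known, it hands over to another section: "AEs with partial dates are described in" Section 5.7.2.

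SAP 5.7.2 then sets these rules, none of which mentions the stop date:

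- Onset year missing: "If the year of onset of the AE is missing, then the AE is considered treatment emergent".
- Only the year known, and equal to the treatment year: "then the AE is considered treatment emergent, and the AE onset date will be set to the study treatment administration date".
- Year and month known, and equal to those of treatment: "then the AE is considered treatment emergent and the AE onset date will be set to the treatment administration date".

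The section gives its purpose: "These rules are intended to lead to a conservative assessment of treatment emergence". Its only rule on AE end dates concerns a missing one: such an AE counts as emergent when its onset is not earlier than the treatment date.

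Protocol 12.4.5 restricts the safety analysis to AEs that occur after the product is given. Protocol section 9 has AEs recorded from the first study procedure onward, and Protocol 4.1 places screening 28 to 2 days before dosing.

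**The concern.** An event that had ended before the injection cannot have started after it, and cannot be a post-dose worsening of something still present. When the stop date shows this, missing onset information leaves no doubt to resolve.

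Two separate faults follow. First, for a wholly unknown onset, SAP 5.6 looks at the stop date and SAP 5.7.2 does not, so the flag depends on which section is programmed. Second, for a partial onset in the injection month or year there is only one rule, in SAP 5.7.2, and that rule can flag a demonstrably pre-dose event as treatment-emergent. At stake is the accuracy of the treatment-emergent counts in a 36-subject trial, and whether two programmers working from the SAP would produce the same table.

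**Working it through.** The plan states no figure on this point, so the check is to apply the rules to test records. The dates are assumed for illustration: injection on 20 March 2016; stop date 10 March 2016, 25 March 2016 or missing; onset wholly missing, year only (2016), or year and month (March 2016).

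| Onset recorded | Stop date | SAP 5.6 | SAP 5.7.2 | Onset used for the flag |
|---|---|---|---|---|
| nothing | 10 March | not emergent | emergent | none given |
| nothing | 25 March | emergent | emergent | none given |
| nothing | missing | emergent | emergent | none given |
| 2016 | 10 March | defers to 5.7.2 | emergent | 20 March |
| 2016 | 25 March or missing | defers to 5.7.2 | emergent | 20 March |
| March 2016 | 10 March | defers to 5.7.2 | emergent | 20 March |
| March 2016 | 25 March or missing | defers to 5.7.2 | emergent | 20 March |

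1. **Conflict between sections.** It appears in one row only: wholly unknown onset with a stop before the injection.
2. **Gap within SAP 5.7.2.** It appears in the two partial-onset rows with the 10 March stop. Stop minus onset used for the flag is 10 March − 20 March = −10 days, so the working onset falls ten days after the event ended. This is not a conflict with the stop-date sentence in SAP 5.6, which does not reach partial dates. It does conflict with the basic definition in SAP 5.6 and with the scope set by Protocol 12.4.5.
3. **Does other text repair it?** The end-date rule covers only missing end dates. Nor can SAP 5.6 act as a later filter for partial onsets: SAP 5.7.2 applies its rules before status is decided and then treats an imputed date as complete, so the start is no longer unknown.
4. **Can such records arise?** Yes. AEs are collected for up to 28 days before dosing.
5. **Size per case.** Protocol 12.4.5 reports incidence as the number and percentage of subjects with the event at least once. With 36 subjects, one subject wrongly counted adds 1/36 = 0.028, or 2.8 percentage points, to that event's incidence.
6. **With a stop-date check placed first.** The three rows with a 10 March stop become not emergent. All other rows keep their present result.

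**The case against.** The best defence is that the rules are meant to be conservative, that they can only over-count and so cannot hide a signal, and that the case is rare. It needs an AE that began and ended before dosing, with its onset incompletely recorded and its stop date recorded. Protocol 9.1.1 asks for actual onset and resolution dates, and Protocol 13.8 provides edit checks and queries. A missing onset year should be rarer still when collection starts at most about four weeks before dosing. Protocol 12.4.5 would also give a programmer grounds to leave out a documented pre-dose event. Finally, no safety-analysis section can be read in the public SAP, so the construction of the tables cannot be checked.

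Most of this stands as a limit on size. It does not remove the fault: conservatism settles doubt, and a recorded pre-dose stop leaves none.

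A reader might infer three stronger things that the documents do not support.

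- That these AEs would be displayed with an onset on the injection day and attributed to the dose. SAP 5.7.2 says that imputed dates serve only to set the flag and that listings keep the recorded partial date. SAP 5.1 computes no study day from an incomplete date. Relationship to treatment is the investigator's judgement (Protocol 9.1.1.2), not something derived from the imputed onset.
- That SAP 5.6 and 5.7.2 contradict each other for partial dates too. SAP 5.6 expressly defers those.
- That many AEs are exposed because many screening days fall in the same calendar month as the injection. That is a share of days, not of AEs, still less of AEs with incomplete onset and a pre-dose stop. The documents give no such count.

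**Conclusion.** The point holds within these bounds. SAP 5.6 and 5.7.2 contradict each other for an AE with wholly unknown onset and a recorded stop before the injection. Separately, SAP 5.7.2 misclassifies an AE whose partial onset matches the injection month or year when its recorded stop is before the injection. The consequence is a wrong treatment-emergent flag and the counts that depend on it, always upward. Efficacy is untouched.

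The number of affected AEs is not known from the documents and is probably small. The 2.8 points per misclassified subject assumes that all 36 planned subjects are treated and that the subject has no genuine post-dose event of the same kind. The conclusion also assumes that no redacted SAP text applies a stop-date check. It is a wording fault worth correcting because the correction costs almost nothing.

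**What to change.** In SAP 5.7.2, ahead of every rule that defaults to treatment-emergent, state that an AE whose recorded stop date is known to precede treatment administration is not treatment-emergent, whatever is missing from its onset. A stop date is known to precede administration if it is complete and earlier, or if it is partial and its year, or its year and month, is earlier than that of administration. If the stop date is missing, or does not prove a pre-dose end (for example, only the month is known and it is the injection month), the existing conservative rules apply unchanged. Put the same wording in SAP 5.6 so that there is one rule.

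The cost is one sentence in each section and one condition in the AE derivation. No AE whose timing is genuinely uncertain loses its treatment-emergent status.

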#### Missing/Partial End Date for AEs

If the end date is missing and the start date is on or after the date of treatment administration, then the AE is considered treatment emergent

#### Missing/partial dates for prior and concomitant treatments

Missing and partial dates of prior and concomitant treatments will be dealt similarly as partial dates for AEs.

If the year and month of the medication end date are complete and there is no day value, and the month of the medication end date is on or after the month of the study treatment administration date, then the day of the medication end date will be set to the first day of the month. The medication will be assigned as prior or concomitant medication based on the imputed date.

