8.5 Prior and Concomitant Therapy

Prior therapy is defined as prescription and non-prescription medications and preparations, including health and/or dietary supplements taken within 30 days prior to signing the informed consent, but discontinued prior to signing informed consent. Concomitant therapy is defined as prescription and non-prescription medications and preparations,

health and/or dietary supplements other than GS010 IMP that the subject receives during the course of the study (i.e. any time after the signing of informed consent). This includes any medication started prior to signing informed consent and continued after signing.

Idebenone must be completely discontinued for at least 7 days prior to Visit 2 and is prohibited throughout the study. If idebenone has not been discontinued at least 7 days prior to Visit 2 and if the study protocol timeframe between the visits is respected, Visit 2 may be delayed until the 7-day period is complete.

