Concomitant treatments will be defined as any treatments ongoing at the start of study treatment administration or with a start date and time on or after the study treatment administration date and time. Treatments with partial dates will be dealt similarly as AEs with partial dates described in [Section 5.7.2](#). If the start time is missing, then treatments will be assigned ‘concomitant’ based on start date of treatments only if it is on or after the treatment administration date.

[Redacted]

[Redacted]

[Redacted]

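### A medication end date with the day missing is set to the first of the month, so a drug started before injection and ending in the injection month is classed as prior only, even if still taken at injection

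*SAP*

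**What the plan says.** The end-date rule is in SAP section 5.7.2, under the heading on missing and partial dates for prior and concomitant treatments. It applies when the end year and month are complete, the day is absent, and "the month of the medication end date is on or after the month of the study treatment administration date". The injection month itself is therefore covered. In that case "then the day of the medication end date will be set to the first day of the month", and "The medication will be assigned as prior or concomitant medication based on the imputed date".

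The classes are defined in SAP section 5.6. "Prior treatments will be defined as any treatments with start date and time prior to the study treatment administration date and time"; the end date plays no part. "Concomitant treatments will be defined as any treatments ongoing at the start of study treatment administration", and a drug that starts on or after injection is concomitant as well. A drug begun earlier and still running at injection therefore meets both definitions.

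The partial start-date rules for adverse events, also in section 5.7.2, carry a statement of purpose: "These rules are intended to lead to a conservative assessment of treatment emergence". The same paragraph applies those rules to medications. For an onset in the treatment month with the day missing, "then the AE is considered treatment emergent and the AE onset date will be set to the treatment administration date". The first of the month is used there only for onsets in later months.

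**The concern.** The imputed day can change a drug's class in only one month, the injection month. In any later month, every possible day falls after injection. Earlier months are outside the rule. In the one month that matters, day 1 is the choice most likely to fall before injection, so a drug that may have been in use at injection is recorded as already stopped.

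This looks like a start-date convention carried over to end dates. An early imputed start in a later month is harmless. An early imputed end in the injection month removes exposure. At stake is the count of concomitant medications in the safety population, which would be too low. Separately, nothing ties the imputed end to the start date, so a record can end before it begins.

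**Working it through.** The plan gives no figure on this point to reproduce. The check applies the rule literally to calendar dates.

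**Inputs.** Let S be the start date, T the injection date, E the true end date, and E* the imputed end, which is day 1 of the month of E (SAP 5.7.2). From SAP 5.6, a drug is prior if S < T. It is concomitant if S ≥ T, or if it is ongoing at T, taken here as E* ≥ T.

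**Worked cases, injection on 15 March 2016 (illustrative date), end day missing.**

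- Start 10 January, true stop 25 March: E* = 1 March, before T. Classed prior only; in truth also concomitant. Wrong.
- Start 5 March, true stop 25 March: E* = 1 March. Classed prior only, and the end precedes the start. Wrong.
- Start 20 March, true stop 28 March: E* = 1 March, before the start. Still concomitant, because S ≥ T.
- Start 10 May, true stop 20 May: E* = 1 May, before the start. Still concomitant.
- Start 10 January, true stop 20 April: E* = 1 April, after T. Concomitant, correct.
- Start and end both in March, both days missing: the start is imputed to 15 March and the end to 1 March. The dates are reversed, but the drug is concomitant through its start date.

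**How often the label is wrong, for drugs started before the injection month and ending in it.** Assume that every injection day and every stop day in a month of L days is equally likely, and that a stop on the injection day counts as still taken.

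- Pairs still taken at injection: L(L+1)/2.
- Of these, mislabelled (all but injections on day 1): L(L+1)/2 − L = L(L−1)/2.
- Over the months of 2016, still taken: 7 × 496 + 4 × 465 + 435 = 5767.
- Mislabelled: 7 × 465 + 4 × 435 + 406 = 5401, and 5401/5767 = 93.7%.
- Pairs that stopped before injection: also 5401, all correctly labelled prior only.
- Share of all labels that are wrong: 5401/(5767 + 5401) = 5401/11168 = 48.4%. With injection on day 15 of a 31-day month it is 17/31 = 55%.

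**Date reversal.** For a known start and a true stop in the same month, E* precedes the start unless the start is on day 1. The count is the same: 5401 of 5767 pairs.

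**Last-day imputation on the same grid.** None of the 5767 still-taken pairs is classed prior only, and none of the 5767 same-month pairs is reversed. All 5401 pairs that stopped before injection become concomitant. On this grid the total number of wrong labels is unchanged at 5401 of 11168; what changes is their direction, from under-counting to over-counting.

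**The case against.** Several points can fairly be made for the plan.

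- The scope is narrow. A drug that starts, or is imputed to start, on or after injection is concomitant whatever its end date. This stands. It would be wrong to say that every partial end date in the injection month is misclassified, or that a record with both days missing is.
- A reversed end date has no visible consequence of its own. SAP section 9.4.2 counts subjects by drug class and preferred term, and no duration of medication is defined in the text available. This stands too.
- The stated conservative aim concerns treatment emergence of adverse events. The paragraph extends the rules to medications but does not separately state such an aim for concomitant status. This stands in part: the end-date rule departs from the approach of the rules it is said to resemble, rather than breaking an explicit promise about medications.
- No record disappears. A mislabelled drug is still prior by definition, so it remains in the summaries and listings. This stands, but the concomitant count is still too low wherever the two classes are shown apart.

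A reader might infer something more serious. The protocol states that "Idebenone must be completely discontinued for at least 7 days prior to Visit 2 and is prohibited throughout the study", so a partial idebenone end date set to day 1 might seem to hide a deviation and keep a subject in the per-protocol set. The documents do not support this. The prior or concomitant label is anchored on injection and does not measure a washout counted back from Visit 2. Major deviations are decided at the masked data review (SAP section 9.2), and nothing derives them from the imputed label. Listings show the recorded partial dates, so reviewers would not see a false day 1.

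The other provisions in section 5.7.2 do not rescue the rule. The general instruction to treat medication dates like adverse event dates is followed by the specific end-date sentence. The adverse event end-date rule concerns missing end dates for events starting on or after treatment.

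**Conclusion.** The concern holds in limited form. As written, the rule gives a wrong label to a drug started before injection and still taken at injection, if its end date falls in the injection month with the day missing and injection was not on the 1st. It always errs towards under-counting concomitant use. The 93.7% and 48.4% rest on evenly spread days and apply to that subset alone; they are not estimates for the trial. The number of such records is not in the documents and is likely small.

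Only the prior and concomitant treatment summaries are affected. No efficacy estimate, sample size or per-protocol membership is shown to depend on the label. This is a minor correction, worth making because the rule is wrong in the only month in which it can matter.

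**What to change.** Replace the end-date sentence in SAP section 5.7.2. Where the day is missing, impute the last day of the stated month, or the last-contact date if that is earlier. Never impute an end before the drug's start date (recorded or imputed). Assign prior or concomitant status on the resulting date.

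The cost is one line in the derivation, and some drugs that stopped earlier in the injection month will be counted as concomitant. That is the conservative direction, and a table footnote can say so. The change should be made before the randomization code is broken, because Protocol Appendix V allows no amendment of the SAP after that.

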#### Missing severity or relationship to study treatment/study procedure of an AE

If the intensity of an AE is missing, an intensity of “severe” will be imputed.

If the relationship to study treatment/study procedure is missing, a relationship of “probable” will be imputed.

#### Missing/Partial End Date for Other Safety Variables

For other safety variables a similar approach for missing end dates will be followed in the data derivation of the Analysis Data Model (ADaM) specifications.

The same approach will be undertaken for the imputation of missing/partial end dates related to prior and concomitant treatments.

